University of Wisconsin-Madison

Study #: 2017-0755

IRB Approval Date: 7/17/2017

**COMBINATION VERSUS MONOTHERAPY WITH ALPHA-BLOCKERS AND
ANTICHOLINERGICS FOR THE RELIEF OF URINARY STENT SYMPTOMS - A
RANDOMIZED CONTROL TRIAL**

Principal Investigator: [name]

Co-Investigator: [name]; [name]; [name]

University of Wisconsin-Madison, School of Medicine and Public Health, Department of Urology

BACKGROUND AND SIGNIFICANCE

Ureteral stents are used to relieve acute or chronic obstruction of the upper urinary tract, or used as a prophylactic measure following instrumentation or surgery involving the ureter. Ureteral stents work by re-establishing or maintaining patency of the ureter in conditions of obstruction or injury. Stents passively dilate the ureter, allowing urine to flow both through and around the stent, and are indicated when there is ureteral obstruction with or without renal insufficiency, secondary to nephrolithiasis, malignancy, or other pathologic processes. Additionally, they can be used as a prophylactic measure after endoscopic procedures involving the ureter, or surgical repair of the ureter such as in ureteral anastomoses.

Unfortunately, despite their use since the late 60's, stent related symptoms are common in patients after stent insertion and continue to be a challenge to manage. Overall quality of life is impaired in 45% - 80% of patients with ureteral stents in place ¹. Stent related symptoms occur in up to 80% of patients following stent insertion. These include: storage urinary symptoms such as urinary frequency, urgency, nocturia, dysuria, hematuria, stent colic (flank/SP pain), and incomplete emptying or urinary incontinence. To date, various methods have been investigated and employed in an effort to alleviate these symptoms, from various stent designs to pharmacotherapy. With respect to pharmacologic management of stent symptoms, various agents have been investigated, including intravesical pharmacologic therapy ², periureteral injection of botox ³, selective alpha-1 blockers ⁴, and anticholinergic agents ⁵.

University of Wisconsin-Madison

Study #: 2017-0755

IRB Approval Date: 7/17/2017

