Patients who will be undergoing urinary stent insertion during the management of renal or ureteral stones, or other conditions requiring endoscopy will be randomized into the combination or monotherapy arm, based on a computer generated randomization scheme, and will be enrolled into the study arm in a blinded manner. The study is intended to be double-blinded. The drug kit will be linked to the randomization number and both the investigator and patient will thus be blinded to the treatment. All patients will be required to provide a signed informed consent, which outlines the differences in the two treatment arms and study objectives. Patients will be provided the corresponding pills in pre-filled vials, based on their group assignment. Initially, the study used a 7-day treatment regimen. Patients in the monotherapy arm were given a set of Tamsulosin and placebo pills, while the combination therapy arm were given a set of Tamsulosin and Tolderodine ER, with sufficient quantities for 7 days. Pill counts were obtained at the end of the follow-up period to ensure compliance. All patients enrolled into the study were asked to complete the USSQ prior to stent insertion to serve as a baseline assessment of urinary symptoms, and again at 24 hours, 5 days after stent insertion and post stent removal. In the 7-day regimen, 80 patients were enrolled and completed the study (15 patients enrolled but withdrawn, 95 patients in total).

University of Wisconsin-Madison

Study #: 2017-0755

IRB Approval Date: 7/17/2017

The data analysis shows no benefit from being on combination therapy likely secondary to the short duration of therapy.

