Once appropriate informed consent has been obtained, a complete medical history including a detailed urologic history will be completed. The subject will be randomized to one of the two arms (tamsulosin + placebo versus tamsulosin + tolterodine) using a computerized randomization scheme.

STUDY DRUG/INTERVENTION

The study drugs of interest are Tamsulosin and Tolterodine ER, both of which are routinely used in urology. The UW pharmacy will supply the study drugs and placebo. Each of the study drugs and placebo will be provided in standard drug vials. Under the original, 7-day study treatment regimen, each vial contained 7 pills each. In 2014, the study was amended to add a 21-day treatment regimen. This replacement study will use only the 21-day treatment regimen, and the drug vials will contain 21 pills each. The placebo capsule will be similar in color and appearance to the Tolterodine capsule, and will be provided by the UW pharmacy. Patients may continue to use any prior medications concurrently with either of the study drugs, and no washout period is necessary.

TAMSULOSIN

University of Wisconsin-Madison
Study #: 2017-0755
IRB Approval Date: 7/17/2017

Tamsulosin is a selective α_{1a} -blocker (Flomax™), generic since 2009. It is an antagonist of α_1 -mediated contraction of prostate, bladder and proximal urethral smooth muscle, and as such, reduces urethral pressure and resistance, bladder outlet resistance, bladder hyperactivity, and consequently LUTS. Its adverse effects include headache, dizziness, asthenia, nasal congestion, retrograde ejaculation, and a rare reversible condition known as floppy iris syndrome, which is only relevant if patients are undergoing cataract surgery.

TOLTERODINE ER

Tolterodine ER is an anticholinergic (antimuscurinic) agent, which is used as one of the first line agents for detrusor overactivity. It is given as once-daily dosing for overactive bladder symptoms, and even used in BPH patients exhibiting bladder symptoms. Its side-effects include xerostomia, xerophthalmia, gastroparesis, constipation, drowsiness, acute urinary retention, but unlike other drugs of this class, e.g. oxybutynin, tolterodine ER causes little to no cognitive impairment due to its larger molecular weight which precludes crossing of the BBB.

SAFETY AND MONITORING

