Regular inquiries of study flow, pertaining to patient recruitment, randomization, patient compliance (with medication and completing questionnaires) and adverse events will be scheduled to occur after the first week and subsequently every two weeks during the active patient enlistment phase. Any adverse events/side effects will be monitored as per

University of Wisconsin-Madison

Study #: 2017-0755

IRB Approval Date: 7/17/2017

standard protocol in clinical use. Patients will be instructed to report any untoward reactions to the study drugs to the urology clinic or on-call urology staff.

No significant adverse events are anticipated with either of the study drugs, as they are routinely used in everyday urology practice. The patient will report side effects if and when they occur; the drug will be stopped if continuation is deemed inappropriate. Any adverse events or unanticipated problems will be recorded and the offending drug will be stopped, and the patient counseled accordingly. If a patient has side effects that precludes their ongoing participation in the study, they will be withdrawn and considered a study drop-out. All measures will be in effect to prevent breaches of confidentiality and/or emotional upset.

Patients are instructed to contact their treating surgeon if they have symptoms that may require placing the stent or having surgery sooner than expected. The surgeons who perform these procedures are also members of the study team, and will ensure that all patients' clinical care will not be influenced due to study participation. We confirm that study participation will not delay needed clinical care in the event that an enrolled subject requires stent placement sooner than anticipated. We will only include patients whose stent placement will not be delayed as a result of study participation. If the patient has the stent placed in the interim or has discontinued medications, he or she will be excluded from the study.

University of Wisconsin-Madison

Study #: 2017-0755

IRB Approval Date: 7/17/2017

STATISTICAL ANALYSIS & POWER CALCULATIONS:

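### Side-effect capture rests on patients' spontaneous reports, with no solicited questions at the USSQ time points and no adverse-event summary by arm, so the harms of adding tolterodine ER are likely to be under-ascertained

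*Combined protocol and SAP*

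**What the plan says.** Safety and Monitoring gives one described route from patient to study: "The patient will report side effects if and when they occur; the drug will be stopped if continuation is deemed inappropriate". The route runs through the patient's own initiative: "Patients will be instructed to report any untoward reactions to the study drugs to the urology clinic or on-call urology staff". What is reported is then kept: "Any adverse events or unanticipated problems will be recorded and the offending drug will be stopped, and the patient counseled accordingly". No checklist, grading scale or time point for adverse events is given.

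The same section has two other statements. One schedules oversight: "Regular inquiries of study flow, pertaining to patient recruitment, randomization, patient compliance (with medication and completing questionnaires) and adverse events will be scheduled", with the timing "to occur after the first week and subsequently every two weeks during the active patient enlistment phase". The other says that adverse events will be monitored in the way usual in clinical practice, without describing it.

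The Tolterodine ER section names what to expect: "Its side-effects include xerostomia, xerophthalmia, gastroparesis, constipation, drowsiness, acute urinary retention". Under Study Activities, every patient on the 21-day regimen completes the USSQ at baseline, before stent insertion, at 24 hours, at day 5 and after stent removal, and pills are counted at the end of follow-up. None of these occasions is linked to a side-effect question. Statistical Analysis & Power Calculations covers USSQ responses and score changes; it mentions no analysis or table of adverse events.

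**The concern.** The trial compares tamsulosin plus tolterodine ER with tamsulosin plus placebo and aims to show that the addition helps. Anyone using the result will weigh symptom benefit against the side effects of the added drug. Mild effects such as dry mouth or constipation are the kind that patients often do not phone in, so a system resting on unprompted calls is likely to miss some of them. With no table by arm planned, even the events that are recorded may never be compared. Side effects that end participation are handled as drop-outs, so without reasons by arm they can disappear into attrition. The present regimen also lasts 21 days instead of 7, with two weeks of dosing before surgery, so there is more time on drug in which effects can occur.

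**Working it through.** **1. What the text supports.**
- Described route from patient to study: spontaneous reporting to the clinic or on-call staff.
- Scheduled inquiries: listed alongside recruitment and randomization, on a clock that follows the enrolment phase and not each patient's 21 days. They read as study-level oversight, but the text does not say whether patients are asked.
- Routine clinical monitoring: cited, not described.
- Occasions on which every patient already supplies data: five USSQ time points and one pill count. Side-effect questions at these: none.
- Planned adverse-event comparison by arm: none.

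**2. The plan's own figure.** The only calculation in the documents concerns efficacy: a 4-point difference, SD 6.5, two-sided 0.05, power 0.80. The normal approximation gives n = 2 × (1.96 + 0.84)² × 6.5² / 4² ≈ 41.5, so 42 per arm. The t-test version gives 42.43, so 43 per arm, which is the stated figure. The plan adopts 53 per arm, for which power is about 0.88. Side-effect capture does not enter this calculation.

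**3. Illustration of under-ascertainment.** The documents give no side-effect rates and no capture rate, so everything here is assumed. Let the true proportions be p_C (control) and p_T (combination), and let a fraction s of events be captured, equal in both arms.
- Observed difference = s × (p_T − p_C), which shrinks with s.
- Observed ratio = (s × p_T) / (s × p_C) = p_T / p_C, which does not change in expectation.
- Expected counts = 53 × s × p.
- Power: two-sided 0.05 normal-approximation test of two proportions, 53 per arm.

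| True rates (control vs combination) | s | Observed difference (points) | Expected events | Power |
|---|---|---|---|---|
| 10% vs 30% | 1 | 20 | 5.3 vs 15.9 | 0.74 |
| 10% vs 30% | 0.75 | 15 | 4.0 vs 11.9 | 0.58 |
| 10% vs 30% | 0.5 | 10 | 2.7 vs 7.9 | 0.40 |
| 10% vs 30% | 0.25 | 5 | 1.3 vs 4.0 | 0.22 |
| 5% vs 15% | 1 | 10 | 2.7 vs 7.9 | 0.40 |
| 5% vs 15% | 0.5 | 5 | 1.3 vs 4.0 | 0.22 |

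The ratio is 3 in every row. What is lost is the absolute difference and the chance of seeing it. At the lower rates a trial of this size would probably miss the difference even with full capture.

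**The case against.** The strongest reply is that the plan does not rely on volunteered reports alone. Adverse events are named in the scheduled inquiries and are to be monitored as in ordinary practice, and those that come to light are recorded. That is fair: a reader might infer that side effects are captured only when volunteered, and the text does not go that far. But neither additional route has a described method, instrument or time point for the individual patient.

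Other stronger readings also fail:
- **That the trial's conclusion is biased toward the combination.** Benefit is defined by USSQ scores, which side-effect capture does not alter. No tolerability comparison is planned that could be biased; its absence is the gap.
- **That an undercount is established.** It is a reasonable expectation, not a documented fact. The matched placebo and double-blinding make equal reporting between arms plausible, and then the ratio is preserved. Differential reporting is possible but not shown.
- **That past withdrawals show a tolerability problem.** In the 7-day regimen "80 patients were enrolled and completed the study (15 patients enrolled but withdrawn, 95 patients in total", that is 15/95 = 15.8%. No reasons or arms are given, and the protocol also removes patients for other causes, such as a stent placed in the interim. The figure supports asking for reasons by arm and nothing more.
- **That drug-related retention will be mistaken for a stent symptom.** The Background lists, among stent symptoms, "stent colic (flank/SP pain), and incomplete emptying or urinary incontinence", which overlaps with retention as a drug effect. During the two-week lead-in, however, the study stent is not yet in place. In the stented week a direct question is just as ambiguous for the single patient; only a comparison between arms helps.

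**Conclusion.** The point holds as a cheap improvement to harm assessment. The patient-level method that the plan describes is spontaneous reporting, the expected effects are already listed, existing time points are not used to ask about them, and no summary by arm is planned. Under-ascertainment is therefore likely, and with it an understated absolute difference between arms. Its size cannot be derived from the documents. With equal capture in both arms the difference shrinks in proportion to the fraction captured (half captured, half the difference) and the expected ratio stays the same. The primary USSQ comparison and the planned 53 per arm stand. The conclusion assumes that the scheduled inquiries do not already put a fixed set of questions to each patient; the sponsor can settle that in one sentence.

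**What to change.** - At the existing USSQ time points (baseline, before stent insertion, 24 hours, day 5, after removal), and only once the USSQ has been completed, put the same yes/no list to every patient in both arms, under blinding, with the onset date of each effect. Take the list from the study-drug sections, including all six tolterodine ER effects in lay wording. The baseline answers separate existing complaints from new ones.
- Keep spontaneous reporting between time points. The list would not detect an acute problem during the two-week lead-in, so it supplements that route and does not replace it.
- Add to the statistical section a table of each effect by arm, with reasons for withdrawal by arm, presented beside the efficacy result. It should be descriptive, since the trial is not sized for it.
- State in Safety and Monitoring whether the scheduled inquiries include asking patients, and what the routine clinical monitoring consists of.

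The cost is one short extra form at time points that already exist; how the USSQ is administered is not stated, so the form should follow the same mode. More mild events will be recorded. There is also a small risk that questions about effects such as dry mouth prompt guesses about allocation in a trial with a subjective primary questionnaire. Asking after the USSQ reduces that risk but does not remove it for later time points. The sample size and the primary analysis do not change.

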In 2014, a change of protocol was approved that extended the study treatment to 21 days. Our sample size calculation in the 21-day regimen was based on the recommended sample size calculations by the original developers of the USSQ ¹. The authors' calculations were based on the results of their validation studies that compared mean domain score and standard deviation differences between stented and control patients, using a 2-tailed test ($p < 0.05$). The percentage change (15%) translates to an absolute change in score by 4 points. Additionally, we extrapolated data from a recent meta-analysis evaluating the efficacy of tamsulosin to relieve stent related symptoms, which showed a mean standard deviation of 6.5 points between the tamsulosin and placebo arm ⁴ to confirm the previous authors' sample size. With an expected decrease of 4 points with the combination therapy, and an assumption of similar standard deviation (6.5), a two-tailed t-test ($p = 0.05$) and power of 0.80, our calculation yielded 43 patients per arm. Given the relatively similar numbers from the two calculations, we opted to use the more conservative sample size of 53 patients per arm as the data collection endpoint.

We are assessing for both an absolute and relative change in the USSQ scores.

1. We will be assessing for a relative change of 4 actual points (which translates to a 15% change, as per Joshi et al's validation study) within each group from immediately post stent insertion at 24 hours compared to day 5.
2. We will also assess for a change in scores between groups, i.e. comparing the mean intra-group score change as described in 1 (i.e., immediately post stent insertion at 24 hours compared to day 5).

University of Wisconsin-Madison
Study #: 2017-0755
IRB Approval Date: 7/17/2017

The questionnaire responses will be analyzed using cross tabulations and descriptive statistics to assess differences between groups. Paired *t*-tests will be used to assess within-group change in scores from the USSQ (comparison between post-op, i.e. at 48 hours, and day 5) and other discriminant properties. *T*-tests will be used to assess inter-group score changes.

The intent-to-treat principle will be employed in the event subjects have to withdraw from their assigned group, although this is not expected given that both treatment medications are used extensively in urology, and both treatment regimens are occasionally employed based on anecdotal physician experience.

DATA SECURITY:

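### Randomised patients who stop medication or are stented early are to be excluded, intent-to-treat is promised for withdrawals, and the two rules are not reconciled

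*Combined protocol and SAP*

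**What the plan says.** All places are in the combined protocol and SAP.

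- **Patient Screening and Recruitment.** After consent and a medical history, "The subject will be randomized to one of the two arms".
- **Study Activities, 21-day regimen.** Study drug starts two weeks before surgery and continues for the week the stent is in place. The USSQ is completed before drug, before stenting, at 24 hours and 5 days after insertion, and after removal. A sentence placed after the text on early stent removal makes early termination matter only when the day-5 questionnaire is missing.
- **Safety and Monitoring.** Of patients whose side effects preclude further participation: "they will be withdrawn and considered a study drop-out". At the end of a paragraph on patients who need a stent sooner than scheduled: "If the patient has the stent placed in the interim or has discontinued medications, he or she will be excluded from the study".
- **Statistical Analysis & Power Calculations.** "The intent-to-treat principle will be employed in the event subjects have to withdraw from their assigned group", with the comment "although this is not expected given that both treatment medications are used extensively in urology". For the comparison between arms, t-tests "will be used to assess inter-group score changes", the change being from 24 hours to day 5.

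No section defines an analysis set, questionnaire collection after exclusion, or the handling of missing scores.

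**The concern.** Intent-to-treat means that every randomised patient is followed and analysed in the assigned arm. A rule that excludes patients for something that happens after randomisation works against this, because the reason for exclusion may relate to treatment or symptoms. The arms compared may then no longer be the arms randomised.

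There is a plausible route to imbalance. Only one arm takes tolterodine, and the protocol lists side effects for it, so stops for side effects could differ by arm. The two-week drug period before stenting gives time for this before any outcome score exists.

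At stake are which effect the trial estimates and whether its label is accurate. If the choice between the two rules is left until after unblinding, the main result is also open to selection.

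**Working it through.** **1. The texts side by side**

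| Question | Safety and Monitoring | Statistical section |
|---|---|---|
| Patient stops drug or is stented early | Excluded from the study | Intent-to-treat on withdrawal |
| Meaning of exclusion | Not stated: end of participation, or removal from analysis | Not addressed |
| Period covered | Early stenting: before the scheduled stent. Stopping drug: the pre-stent period or all 21 days, not stated | Not addressed |
| Scores collected afterwards | Not stated | Not stated |

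The exclusion rule can remove a patient in two distinct ways:

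- Follow-up stops, so the 24-hour or day-5 score is never collected. No change score exists, and calling the analysis intent-to-treat cannot supply one.
- Both scores exist, but the patient is removed for being off drug or stented early. The result is an on-treatment comparison.

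Either way randomised patients are left out. The early-termination sentence does not settle the matter, because it follows text on stent removal and does not mention stopped drug or early placement.

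**2. The plan's own sample size**

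Inputs from the statistical section: difference 4, SD 6.5, two-sided 0.05, power 0.80.

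Normal approximation: n = 2 × (1.960 + 0.842)² × (6.5/4)² = 41.4, so 42 per arm. The t-test calculation gives 42.4, so 43, which matches the stated 43. The plan adopts 53 per arm.

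**3. Foreseeable loss**

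Study Activities, 7-day regimen: 15/95 = 15.8%, exact 95% CI 9.1% to 24.7% (sampling error only). Applied to 106 patients, this is 16.7 (9.7 to 26.2), or 8.4 per arm of 53. Reasons, arms and timing relative to randomisation are not given. That regimen also had no two-week pre-stent drug period, so the rate is an illustration only.

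**4. Power after loss**

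Two-sample t-test with noncentrality (4/SD) × √(n/2) and 2n − 2 degrees of freedom. The plan does not say whether 6.5 is the SD of a change score or of a single-visit score. If it is single-visit, the change SD is 6.5 × √(2(1 − ρ)), with ρ an assumed correlation between 24 hours and day 5. At ρ = 0.5 this equals 6.5.

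| Loss | n per arm | SD 5.03 (ρ 0.7) | SD 6.5 | SD 7.69 (ρ 0.3) |
|---|---|---|---|---|
| 0% | 53 | 98.2% | 88.1% | 75.6% |
| 15.8% | 44.6 | 96.0% | 82.0% | 68.1% |
| 24.7% | 39.9 | 93.9% | 77.5% | 63.1% |

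The cost is about 2 to 8 percentage points at 15.8% loss and about 4 to 13 at 24.7%.

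**5. Power when off-drug patients are kept**

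All 53 per arm analysed, SD 6.5, with 15.8% of the combination arm off drug:

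- They gain nothing: 4 × (1 − 0.158) = 3.37 points, power 75.3%. Reaching 80% would need 60 per arm.
- They keep half the benefit: 4 × (1 − 0.079) = 3.68 points, power 82.4%.

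On these assumptions the two rules target different effects: 4 points in patients who stay on treatment, and 3.37 to 3.68 in all randomised.

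**The case against.** The exclusion sentence sits in a safety section, in a paragraph assuring that care will not be delayed. The statistical section is the only text on analysis, and it says intent-to-treat. A fair reader could conclude that it governs analysis and that exclusion means only the end of participation. This stands in part: a reader might infer that the plan removes these patients from the analysis and therefore mislabels its result, but the documents do not say so. What remains on the milder reading is a gap: without follow-up after exclusion, the scores that intent-to-treat needs are not collected.

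A t-test on change uses only patients with both scores in any case. That is true and reflects the missing rule for absent scores. The exclusion rule may add to that loss, and may also remove patients who do have scores.

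A reader might infer that 15 withdrawals among 95 contradict the statement that withdrawal is not expected. This is not shown. The plan speaks of withdrawal from the assigned group, while the 15 are described only as enrolled and then withdrawn. Some may never have been randomised or taken drug.

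A reader might also infer bias in favour of combination therapy. The documents do not support a direction. The trial is double-blind, "The placebo capsule will be similar in color and appearance to the Tolterodine capsule", both arms take tamsulosin with side effects of its own, and nothing links early stenting to arm.

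Finally, the statistical section calls 53 per arm the data collection endpoint. If that means 53 with data, the power loss in step 4 does not arise. The planned enrolment of 106 = 2 × 53 points the other way.

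**Conclusion.** The concern holds in conditional form. The exclusion rule and the intent-to-treat promise both reach randomised patients and are not reconciled. If the exclusion rule governs follow-up or analysis, the main comparison omits randomised patients and could not be called intent-to-treat. If the statistical section governs analysis, the plan still lacks the follow-up and missing-score rules needed to carry it out.

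The size and direction of any bias cannot be estimated from the documents, and it may be nil. Loss of power is secondary. With 6.5 as the change-score SD, power falls from 88.1% to 82.0% at 15.8% loss and to 77.5% at 24.7%, on the assumption that the 7-day rate transfers and that 53 per arm counts patients enrolled. It would be too strong to say that the trial is underpowered or its result biased. The conflict should be fixed because it is plain in the text and cheap to resolve.

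**What to change.** Reconcile the 21-day text in Study Activities, the exclusion sentence in Safety and Monitoring, and the intent-to-treat paragraph, by separating stopping study drug from leaving the study. Suggested wording:

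> *Patients who stop study drug or are stented earlier than planned remain in follow-up if they agree, complete the 24-hour and day-5 USSQ after stent insertion, and are analysed in their randomised arm. An on-treatment comparison is shown only as a sensitivity analysis.*

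Before unblinding, also state how missing scores are handled and how patients who never receive a stent are treated, since they have no stent-symptom score. Report withdrawals by arm, reason and time. Clinical decisions on stopping drug or on the timing of stenting are unchanged.

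Costs:

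- An amendment, and two existing questionnaires from about 8 more patients per arm at the 7-day loss rate.
- Enrolment on this regimen began on 10/29/2014, 992 days before the approval date of 7/17/2017. How many patients have been excluded, and whether this rule applied throughout, is not stated. Scores from patients already excluded may be unrecoverable, so the date of the change should be disclosed.
- Off-drug patients dilute the effect. Restate power on the intent-to-treat basis (step 5: about 75% or 82% at 53 per arm, depending on the benefit retained) rather than enlarge the sample.
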